6.2 Sample Size

No formal sample size formulation was performed. As requested by sponsor, a total of 10 subjects (approximately equal distribution of sex) will be enrolled with the goal of completing a minimum of 6 subjects.

6.3 Statistical Analysis

All statistical analyses will be conducted using SAS for Windows (version 9.2, or higher, Cary, NC) and/or R 3.3.1 (R Core Team 2016). The data will be analyzed for the modified intent-to-treat population, which will include all subjects who complete all test visits. Subject data may also be excluded for the following reasons and possibly others:

• Non-compliance by the subject, including, but not limited to:

- o Missing appointments
- Use of prohibited drugs or any products thought to alter the outcome variables during the study
- o Not adhering to instructions as outlined in the protocol

All decisions regarding subject population and data inclusion will be documented prior to database lock.

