5.8 Early Termination Procedures

The term "Early Termination" refers to a subject's non-completion of the study. Should a subject decide to withdraw, all efforts will be made to complete and report observations as thoroughly as possible. In the event that a subject is withdrawn from the study, the reason for the withdrawal and the party who initiated the withdrawal (subject or Clinical Investigator) will be documented. Should the subject decide to withdraw, documentation of early termination and any AEs and concomitant medication use should be recorded.

The primary reason for a subject withdrawing prematurely should be selected from the following standard categories:

Adverse Event – event which results in discontinuation of the study product by the subject or that in the judgment of the Clinical Investigator for the best interest of the

subject requires discontinuation of study product (includes all categories of study product relatedness; Not Related, Unlikely, Possibly, Probably, and Definitely).

Death – death of the subject.

Withdrawal of Consent – subject desires to withdraw from further participation in the study in the absence of a medical need to withdraw determined by the Clinical Investigator.

Lost to Follow-Up – subject did not return for one or more follow-up visit(s) following dispensing of study product and could not be contacted thereafter. The reason for withdrawal was unknown and could not be documented.

Other – causes of premature termination from the study other than the above, such as theft or loss of study products, termination of study by Sponsor, etc.

6. Data Analysis and Statistical Methods

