6.1 Outcome Variables

The outcome variables will include the following parameters for serum strontium at all three doses:

- Incremental area under the curve (iAUC) for serum strontium from pre-product consumption (t = -0.25 h) to 12 h (iAUC-_{0.25-12h})
- iAUC for serum strontium from pre-product consumption (t = -0.25 h) to infinity (AUC_{0- ∞})
- Maximum plasma concentration (Cmax)
- Time to Cmax (Tmax)
- Rate of elimination (λ_z)
- Half life $(t_{1/2})$
- Estimated fraction of the dose which is absorbed

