6.5 Outcome Analysis

Descriptive statistics (i.e. number of subjects, minimum and maximum, median, interquartile limits, mean, and SEM) will be presented for all the continuous outcomes for each dose level.

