6.6 Safety Analysis

Safety will be assessed by AEs reported by subjects, as well as assessment of vital signs and body weight.

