7.3 Adverse Event Monitoring

In a consensus view of guidelines for the design, conduct and reporting of human intervention studies to evaluate the health benefits of foods, an International Life Sciences Institute Europe Expert Group defines an AE as "any untoward medical occurrence or undesirable clinical experience in a participant in a clinical trial, whether or not considered related to the intervention" (Welch 2011). This includes any occurrence that is new in onset or aggravated in severity or frequency from the baseline condition, or abnormal results of diagnostic procedures (including laboratory test abnormalities where applicable). Therefore, clinical observations, including responses to the question, "Have there been in any changes in your health or medications since you were last asked?" will be collected at Visits 2 through 4. These observations will be reviewed for assessment of AE, including severity and potential relationship to the intervention as determined by the Clinical Investigator.

Events should be considered AEs if they:

- Result in discontinuation from the study,
- Require treatment or any other therapeutic intervention,
- Require further diagnostic evaluation (excluding a repetition of the same procedure to confirm the abnormality),
- Are associated with clinical signs or symptoms judged by the Clinical Investigator to have a significant clinical impact.

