7.3.5 Electronic CRF Recording of Adverse Events

All AEs will be recorded on the AE eCRF page. For subjects who have an ongoing AE at their final study visit, a follow-up AE eCRF page will be completed after 30 d. All SAEs must be recorded on the AE and SAE eCRF page.

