8.5 Withdrawal of Subjects from the Study

Subjects may be removed from the study for any of the following reasons:

- A subject requests discontinuation;
- The Clinical Investigator initiates removal for medical or compliance reasons;
- Occurrence of any AE or condition that could, in the Clinical Investigator's opinion, interfere with the evaluation of the treatment effect of the study product or put the subject at undue risk.

It is understood by all concerned that an excessive rate of withdrawals can render the study uninterpretable, therefore, unnecessary withdrawal of subjects should be avoided.

Confidential

Should a subject decide to withdraw, all efforts will be made to complete and report observations as thoroughly as possible. In the event that a subject is withdrawn from the study, the reason for the withdrawal will be documented in the eCRF. Prior to a subject's withdrawal from the study, an attempt will be made to conduct an early termination visit, which will include the clinic visit procedures and AE assessment.

9. Administrative Matters

All references to the Sponsor in this section include all designees e.g., Contract Research Organizations or Consultants acting on behalf of the Sponsor.

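### The only analysis set is a completer set under a modified intent-to-treat label: if subjects withdraw it drops their valid lower-dose PK profiles, and the safety population is left unstated

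*Combined protocol and SAP*

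**What the plan says.** Section 6.3 states: "The data will be analyzed for the modified intent-to-treat population, which will include all subjects who complete all test visits". It then allows further exclusions for non-compliance and possibly other reasons, with decisions documented before database lock. No other set is defined in Section 6; efficacy evaluable and per protocol appear only in the abbreviation list.

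For PK, Section 6.5 says that descriptive statistics "will be presented for all the continuous outcomes for each dose level". No comparison between doses is planned. Section 6.7 rules out imputation and uses observed data only, which does not bring non-completers back into the set.

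For safety, Section 6.6 says: "Safety will be assessed by AEs reported by subjects, as well as assessment of vital signs and body weight". It names no population.

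Section 5.2 gives every subject the low, medium and high dose in that order at Visits 2, 3 and 4, unblinded. Section 6.2 plans 10 subjects, with a goal of at least 6 completing. Section 2 says that this product has not been in a clinical trial before.

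**The concern.** A set limited to subjects who finish every test visit is a completer set, whatever it is called. Two things follow.

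**PK.** A subject who withdraws after Visit 2 or Visit 3 has already provided a full 12-hour profile at one or two doses. The by-dose summaries in 6.5 could use those profiles as they stand, but 6.3 removes them. In a study of 10 subjects that is a material share of the lower-dose data.

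**Safety.** Since 6.3 speaks of the data without qualification and 6.6 names no population, the plan does not say whose AEs are tabulated. Section 7.3 counts as AEs those events that "Result in discontinuation from the study", and Section 5.8 has a withdrawal category for an AE, described as an "event which results in discontinuation of the study product by the subject". If the completer set governed the AE table, the number of AEs leading to withdrawal would be zero by construction. In a first trial of the product, with ascending doses, the AE summary should plainly cover everyone dosed.

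**Working it through.** There is no sample-size calculation to reproduce: Section 6.2 says none was done. The inputs are 10 subjects dosed (6.2), a completion goal of 6 (6.2), the fixed order low, medium, high (5.2), and by-dose description only (6.5). The documents give no withdrawal rate, so the number withdrawing is varied over 1, 2 and 4. Four is what the completion goal implies (10 − 6); it is neither a floor nor an expectation.

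**PK.** Let *a* subjects withdraw after a completed low-dose visit and *b* after a completed medium-dose visit, with *k* = *a* + *b*.

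- Completer rule: n = 10 − *k* at every dose, so 3(10 − *k*) profiles are used.
- All evaluable profiles by dose: n = 10 (low), 10 − *a* (medium), 10 − *k* (high), so 30 − 2*a* − *b* profiles are collected.
- Unused profiles: (30 − 2*a* − *b*) − 3(10 − *a* − *b*) = *a* + 2*b*.
- SE under the completer rule relative to the by-dose rule, at equal SD: low √(10/(10 − *k*)); medium √((10 − *a*)/(10 − *k*)); high 1.

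| *k* | Completer n, each dose | SE ratio, low | SE ratio, medium | Profiles collected | Used | Unused |
|---|---|---|---|---|---|---|
| 1 | 9 | √(10/9) = 1.054 | 1.000–1.054 | 28–29 | 27 | 1–2 |
| 2 | 8 | √(10/8) = 1.118 | 1.000–1.118 | 26–28 | 24 | 2–4 |
| 4 | 6 | √(10/6) = 1.291 | 1.000–1.291 | 22–26 | 18 | 4–8 |

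In each range the lower end is everyone leaving after the low dose and the upper end is everyone leaving after the medium dose. In between, *a* = *b* = 1 gives a medium-dose ratio of √(9/8) = 1.061, and *a* = *b* = 2 gives √(8/6) = 1.155. The largest loss shown is 8 of 26 profiles, or 31%. The high-dose n is 9, 8 or 6 under either rule.

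**Safety, if 6.3 is applied literally.** With *w* subjects withdrawing for an AE and *m* completers having an AE, the all-dosed proportion is (*m* + *w*)/10 and the completer proportion is *m*/(10 − *w*). Take *w* = 1; the values of *m* are assumed, because the documents give no AE rate.

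| *m* | All dosed | Completers only |
|---|---|---|
| 0 | 1/10 = 10% | 0/9 = 0% |
| 1 | 2/10 = 20% | 1/9 = 11% |
| 2 | 3/10 = 30% | 2/9 = 22% |
| 3 | 4/10 = 40% | 3/9 = 33% |

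**Which reading of 6.3 applies to safety.** Two passages suggest that it is meant for PK only. Section 6.1 introduces the outcomes with "The outcome variables will include the following parameters for serum strontium at all three doses" and lists only strontium parameters. Section 7.3.5 says "All AEs will be recorded on the AE eCRF page". Section 8.5 says that on withdrawal "all efforts will be made to complete and report observations as thoroughly as possible", and Section 5.8 has a matching provision. Section 8.5 also calls for an attempted early termination visit with AE assessment and the clinic visit procedures, which under 5.6.1 include vital signs and body weight. Those are the safety measures named in 6.6, collected at a visit held only for subjects whom the one defined set excludes. On the other side is the plain wording of 6.3, which makes no exception for safety. The text does not settle the question.

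**The case against.** Analysing the same subjects at every dose is a coherent choice in a crossover. With a fixed ascending order, letting n differ by dose means that differences between the dose summaries partly reflect who stayed. This stands, and is the reason to keep the completer set as a supporting analysis. It does not justify making it the only set, because no within-subject comparison is planned and 6.3 gives no rationale.

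The PK effect is conditional and modest. These are healthy adults with three dosing visits, one or two withdrawals would raise the low-dose SE by 5% to 12%, and nothing inferential changes. This also stands.

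On safety, the PK-only reading of 6.3 is well supported. Withdrawn subjects' AEs are recorded, and SAEs and unexpected AEs go to the IRB, so the events are captured in any case. What stands is that the completer-only AE figures depend on the literal reading and on assumed counts. But recording an event does not define the denominator of the summary or say who is in the table. On the PK-only reading the safety population is simply undefined.

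Section 6.3 also says in the same sentence who is included, so the label misleads no careful reader; renaming the set by itself would be editorial.

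**Conclusion.** The concern holds. The plan has one analysis set, it is a completer set, and it drops usable low- and medium-dose profiles of any subject who withdraws later. The safety population is either unstated or, taken literally, completers only.

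The size depends on withdrawals that have not been predicted. For 1, 2 or 4 withdrawals out of 10 dosed, the low-dose SE rises by about 5%, 12% or 29%, and the medium-dose SE by anything from nothing up to the same figures. This assumes equal SD and withdrawal after a completed visit and before the next dose. The high-dose summary and any inferential conclusion are unaffected, since the PK analysis is descriptive. No PK bias is claimed, because that would need an assumed link between withdrawal and exposure. An AE after the high dose, given at the last visit, is at risk of exclusion only if the subject leaves during that 12-hour visit. If nobody withdraws there is no effect.

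It should be fixed because the correction is cheap and this is the first trial of the product. In an unblinded study the sets are also better settled before any withdrawal than after the subject's data are known.

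**What to change.** Amend Sections 6.3 and 6.6 as follows.

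- Define a safety set of all subjects who take any study product. Tabulate AEs by the most recent dose taken, and show AEs leading to withdrawal.
- Summarise PK at each dose for all subjects with an evaluable profile at that dose.
- Rename the present set completers, and keep it as a supporting analysis for within-subject comparison across doses.

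The cost is wording only: no extra subjects, samples or visits. The drawback is that n may differ between doses in the main PK summary; the completer analysis keeps a view with the same subjects at every dose.

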6.4 Baseline Characteristics

Descriptive statistics [number of subjects, mean, standard error of the mean (SEM), median, interquartile limits, minimum and maximum or frequency counts] will be presented for subject demographics and anthropometric measurements collected at screening/baseline.

6.5 Outcome Analysis

Descriptive statistics (i.e. number of subjects, minimum and maximum, median, interquartile limits, mean, and SEM) will be presented for all the continuous outcomes for each dose level.

6.6 Safety Analysis

Safety will be assessed by AEs reported by subjects, as well as assessment of vital signs and body weight.

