At Visit 2 (day 0), subjects will arrive at the clinic fasted (10-14 h, water only, anchored to the t = -0.25 h blood draw) for the 12-h PK test visit. Subjects will undergo clinic visit procedures including: a review of inclusion/exclusion criteria, concomitant medication/supplement use, body weight, and vital signs assessment. Adverse events (AE) will be assessed and subjects will be queried about study instructions compliance. Additionally, the 24-h Diet Record will be collected and reviewed. A fasting capillary blood glucose will be assessed to confirm fasting status. Eligible subjects will be enrolled and will begin the PK test with the insertion of an intravenous catheter at least 5 min prior to the first blood sampling time. In order to maintain patency of the intravenous catheter, the catheter will be flushed with normal saline solution at least hourly. Blood samples will be drawn by venipuncture if the catheter fails. Blood samples will be obtained at $t = -0.25 \text{ h} \pm 10 \text{ min}$ for the PK analysis of serum strontium, where t = 0 h is the time of study product consumption. Additional blood samples will be collected at all timepoints for backup. Subjects will consume the study product in its entirety within 10 min at t = 0 h. The study product will be dissolved with 100 mL of distilled water with an additional 100 mL of distilled water consumed immediately following. No food will be ingested for the subsequent 2-h period, but ad libitum water consumption will be allowed for the remainder of the visit following study product consumption. Water consumption will be recorded at the subsequent test visits. Blood samples will be obtained for the PK analysis of serum strontium at t = 1 and $2 h \pm 5$ min, where t = 0 h is the start of study product consumption. Subjects will be administered a standard breakfast immediately following the t = 2 h blood draw. Subjects will consume the breakfast meal in its entirety within 30 min.

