Blood samples will be obtained via the indwelling venous catheter or venipuncture at t=3,4,5,6, and $8 \text{ h} \pm 5 \text{ min}$, where t=0 h is the start of study product consumption, for the PK analysis of serum strontium. Subjects will be administered a standard lunch (immediately following the t=6 h blood draw), a standard snack (immediately following the t=8 h blood draw) and a standard dinner (at t=10 h). Subjects will consume the meals/snack in their entirety within 30 min. Following the final blood draw at $t=12 \text{ h} \pm 5 \text{ min}$, AEs will be assessed. Subjects will be dispensed a blank/new 24-h Diet Record to record all food and beverage consumed the day prior to Visit 3 (day 7); as well as a copy of the completed 24-h Diet Record (from day -1) with instructions to replicate the same food and beverage intake as closely as possible the day prior to the subsequent visit. Study instructions will also be provided [(i.e., fasting compliance (10-14 h, water only) and avoidance of alcohol 3 d prior to the subsequent test visits].

At Visits 3 and 4 (days 7 and 14), subjects will return to the clinic for clinic visit procedures (i.e., vital signs; body weight; review inclusion and exclusion criteria for relevant changes, and concomitant medication/supplement use review). AEs will be

assessed and subjects will be queried about study instructions compliance. The 24-h Diet Record will be collected and study staff will review the 24-h Diet Record to compare food and beverage consumption to the day -1 recall for consistency. If the subject's food intake is not consistent from the 24-h Diet Record reviewed at Visit 2 (day 0), the study staff should contact the Project Manager before continuing the visit as the test visit may require rescheduling. Subjects will then crossover to the next sequential dose of study product [medium dose at Visit 3 (day 7) and high dose at Visit 4 (day 14)] and repeat the PK test described above for Visit 2.

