5.6 Clinical Measurements

5.6.1 Clinic Visit Procedures

Clinic visits will include assessment of height (Visit 1; day -7 only), body weight (Visits 1 through 4; days -7 to 14), BMI (Visit 1; day -7 only), evaluation of prior and concomitant medication/supplement use, and a review of inclusion/exclusion criteria (for eligibility at Visit 1 and for potential protocol deviations at subsequent visits).

Standardized vital signs measurements will be assessed at each clinic visit (Visits 1 through 4; days -7 to 14) and will include resting blood pressure and heart rate measured using an automated blood pressure measurement device. Blood pressure will be obtained after the subject has been sitting for at least five min. Systolic and diastolic pressures will be measured once using an appropriate sized cuff (bladder within the cuff must encircle ≥80% of the arm). Clinic staff may take a second blood pressure and heart rate,

if warranted. In the event a second measure is assessed; the second measurement will be recorded in the eCRF. Should elevated blood pressure be present at the screening visit (Visit 1; day -7), one retest will be allowed on a separate day, prior to Visit 2 (day 0).

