5.6.6 Pharmacokinetic Testing

A PK test will be initiated at Visit 2 (day 0). Subjects will be queried to confirm compliance with study instructions. If a subject fails to comply, the subject may be asked to reschedule the test day.

At Visit 2 (day 0), eligible subjects will arrive at the clinic fasted (10-14 h); after clinic visit procedures the PK test will begin with the insertion of an intravenous catheter at least 5 min prior to the first blood sampling time. In order to maintain patency of the intravenous catheter, the catheter will be flushed with 10 mL normal saline solution at least hourly. Should the catheter fail, blood samples will be drawn by venipuncture. Blood samples will be obtained at $t = -0.25 \text{ h} \pm 10 \text{ min}$ for the PK analysis of serum strontium followed by study product administration at t = 0 h. The study product will be dissolved with 100 mL of distilled water with an additional 100 mL of distilled water consumed immediately following. No food will be ingested for the subsequent 2-h period, but *ad libitum* water consumption will be allowed for remainder of visit following study product consumption. Water consumption will be recorded at the subsequent test visits. Blood samples will be obtained for the PK analysis of serum strontium at t = 1 and $2 \text{ h} \pm 5 \text{ min}$, where t = 0 h is the start of study product consumption. Subjects will be administered a standard breakfast immediately following the t = 2 h blood draw. Subjects will consume the breakfast meal in its entirety within 30 min.

Blood samples will be obtained via the indwelling venous catheter or venipuncture at $t=3,\,4,\,5,\,6$, and $8\,h\pm 5\,$ min, where $t=0\,h$ is the start of study product consumption, for the PK analysis of serum strontium. Subjects will be administered a standard lunch (immediately following the $t=6\,h$ blood draw), a standard snack (immediately following the $t=8\,h$ blood draw), and a standard dinner (at $t=10\,h$). Subjects will consume the meals/snack in their entirety within 30 min. The final blood draw will be obtained at $t=12\,h\pm 5\,$ min. The study product at Visits 3 and 4 (days 7 and 14) will be administered within \pm 30 min of the $t=0\,h$ time established at Visit 2 (day 0) and the meals/snack will be replicated.

Pharmacokinetic Test Day Schedule

Test time (t = "x" h)	Visits 2, 3, and 4 (days 0, 7, and 14)

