t = -1.0 h	 Arrive at clinic; Study instructions query; Clinic visit procedures (vitals and body weight); Enrollment (Visit 2; day 0 only); AE assessment; IV inserted (at least 5 min prior to first blood draw)
t = -0.25 h ± 10 min	Blood sample obtained;Additional sample stored
t = 0 h	 Administer assigned study product; Ad libitum water consumption allowed for remainder of visit
$t = 1$ and $2 h \pm 5$ min	Blood sample obtained;Additional sample stored
Immediately following the t = 2 h blood draw	 Administer standard breakfast (consumed in 30 min);
$t = 3, 4, 5, and 6 h \pm 5$ min	Blood sample obtained;Additional sample stored
Immediately following the t = 6 h blood draw	Administer standard lunch (consumed in 30 min)
$t = 8 \text{ h} \pm 5 \text{ min}$	Blood sample obtained;Additional sample stored
Immediately following the t = 8 h blood draw	Administer standard snack (consumed in 30 min)
t = 10 h ± 5 min	Administer standard dinner (consumed in 30 min)
t = 12 h ± 5 min	 Blood sample obtained; Additional sample stored; AE assessment (immediately upon completion of blood sampling); Review study instructions; dispense copy and blank 24-h Diet Record (Visit 2 and 3 only)

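### Vital signs are named as a safety assessment, but every scheduled test-day reading is taken before dosing and none follows the high dose, so they cannot show an acute effect of any dose

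*Combined protocol and SAP*

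**What the plan says.** Section 6.6 is one sentence and names three safety assessments: "Safety will be assessed by AEs reported by subjects, as well as assessment of vital signs and body weight". It gives no time points, no summary method and no comparison.

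Section 5.6.1 sets the frequency: "Standardized vital signs measurements will be assessed at each clinic visit", meaning Visits 1 to 4. Blood pressure is measured once, seated, with an automated device. A repeat is discretionary and has no set time: "Clinic staff may take a second blood pressure and heart rate" if there is reason to.

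Section 5.6.6 sets the order within a test day: "after clinic visit procedures the PK test will begin with the insertion of an intravenous catheter". Its timed schedule, which covers Visits 2, 3 and 4, lists "Clinic visit procedures (vitals and body weight") in the t = -1.0 h row and in no later row.

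The narratives in 5.2 agree. At Visit 2, the procedures on arrival include "a review of inclusion/exclusion criteria, concomitant medication/supplement use, body weight, and vital signs assessment", and enrolment, catheter placement and dosing come afterwards. At Visits 3 and 4, "subjects will return to the clinic for clinic visit procedures (i.e., vital signs; body weight" and other checks), and only then move to the next dose. After dosing, the one scheduled safety step is the adverse-event assessment that follows the t = 12 h draw.

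**The concern.** The study gives single doses and follows serum strontium for 12 h after each. An acute effect on blood pressure or heart rate would be sought in that window, and the subject is in the clinic throughout it. If the readings all precede the dose, the vital-sign data cannot reflect such an effect, whether or not one occurs.

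The background section says that no clinical trial of this product has been done, so these would be its first trial safety data. Without post-dose readings, what is learned about the dosing day depends on answers to an open-ended question, and a symptomless change in blood pressure or heart rate would not be reported that way.

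There is also a labelling risk. The flowchart in 5.3 heads Visits 2, 3 and 4 with the low, medium and high dose and marks the clinic visit, which includes vital signs, under each. Readings tabulated under those headings would carry the name of a dose not yet taken.

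**Working it through.** The plan gives no figure to reproduce. The check sets each scheduled vital-sign reading against each dosing time.

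Inputs:
- Visits with vital signs: Visits 1 to 4 (5.6.1).
- Time on test days: t = -1.0 h (5.6.6 schedule).
- Dosing: t = 0 h at Visit 2 (low), Visit 3 (medium) and Visit 4 (high) (5.2, 5.3).
- Interval between consecutive test visits: 6 to 13 days (5.3, footnote 1).
- Last scheduled visit: Visit 4 (5.2, 5.3).

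| Scheduled reading | Dose given later that day | Most recent dose before the reading | Time since that dose |
|---|---|---|---|
| Visit 1, screening | none | none | not applicable |
| Visit 2, t = -1.0 h | low | none | not applicable |
| Visit 3, t = -1.0 h | medium | low | about 6 to 13 days |
| Visit 4, t = -1.0 h | high | medium | about 6 to 13 days |

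Counts per completing subject:
- Scheduled readings: 1 at screening + 3 on test days = 4.
- Scheduled readings in the 12 h after a dose: 0 + 0 + 0 = 0, so 0 of 3 dosing days has one.
- Scheduled readings at any time after the high dose: 0.

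Four provisions might have supplied a post-dose reading:
- *The visit list in 5.7.2.* Section 5.7 says that its lists are not strictly in order. However, 5.7.2 lists vital signs once per test visit and adverse-event assessment twice, and the timed schedule in 5.6.6 fixes the single vital-sign entry at t = -1.0 h.
- *The second reading in 5.6.1.* It is optional and untimed, so it schedules nothing after dosing.
- *The early termination visit in 8.5.* It includes clinic visit procedures, but it is only attempted, and only for withdrawing subjects. The analysis population in 6.3 is subjects who complete all test visits.
- *The 30-day follow-up in 7.3.5.* It is an adverse-event form for events still ongoing at the final visit and lists no vital signs.

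None of the four schedules a post-dose reading.

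Cost of adding readings: 10 enrolled subjects (6.2) x 3 test days = 30 per added time point, or 60 for two. At the minimum of 6 completers the figures are 6 x 3 = 18 and 36.

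**The case against.** The best case for leaving the plan alone is that this is a pharmacokinetic study. Its only objective is pharmacokinetic, 6.1 lists only serum strontium parameters, and the by-dose summaries in 6.5 cover those outcomes. Section 6.6 does not claim that vital signs test for an acute effect. Subjects are in the clinic for 12 h after each dose and are asked about adverse events at the start and end of each visit, including after the last draw on the high-dose day. The adverse-event definition in 7.3 takes in abnormal diagnostic results. Added readings would also be hard to interpret: there is no untreated day, the study is unblinded, the dose order is fixed and ascending, and only 6 to 10 subjects are expected. A change from a fasted morning reading to one at t = 12 h, about 2 h after dinner starts, mixes any product effect with meals, possible coffee or tea, and time of day.

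Much of this stands. It limits the point to safety description and means that added readings cannot support attribution to the product. It does not put a scheduled reading after any dose.

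Some stronger readings are tempting, but the documents do not support them:
- *That vital signs can never be taken after dosing.* The optional repeat and the early termination visit allow it; the accurate statement is that none is scheduled.
- *That the readings are uninformative.* Those at Visits 3 and 4 could show an effect persisting 6 to 13 days after the low or medium dose.
- *That acute safety is not monitored.* The adverse-event enquiry covers the dosing day.
- *That the report will present a misleading by-dose vital-sign table.* Section 6.6 plans no such table, so this is a risk inferred from the flowchart headings.
- *That the product affects blood pressure or heart rate.* The documents report no such effect.

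**Conclusion.** The point holds for the schedule as written: 0 of 3 dosing days has a scheduled post-dose vital-sign reading, and none is scheduled at any time after the high dose. The scheduled vital signs can describe subjects before each dose and, for the low and medium doses, their state 6 to 13 days later. They cannot show an acute effect of any dose.

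The conclusion rests on the timed schedule in 5.6.6 being followed, and needs no assumption about how long an effect might last. The documents give no such figure, so the size of the problem is the count of readings. It should be corrected because the remedy is cheap and changes what the trial can report about the dosing day, but the pharmacokinetic results do not depend on it.

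**What to change.** Add blood pressure and heart rate, by the method in 5.6.1, at existing draw times on each test day:
- at least one early reading before breakfast, for example with the t = 2 h draw, when the subject is still fasted;
- one at t = 12 h.

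The early reading matters because a 12 h reading alone could miss a transient effect and is the one most affected by meals and time of day. Enter the readings in 5.3, 5.6.6 and 5.7.2.

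In 6.6, summarise the change from the same visit's pre-dose value by dose, descriptively only. State the limits there: no untreated day, a fixed dose order, and a 12 h value affected by meals and time of day. Replicated meals and dosing within 30 min of the Visit 2 clock time (5.6.6) put the readings at similar clock times across the three doses, but do not remove these limits.

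If no reading is added, state in 6.6 that:
- scheduled vital signs are pre-dose only and do not assess dosing-day effects;
- they must not be labelled as values under that visit's dose;
- none follows the high dose.

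The cost is about 30 automated cuff readings per added time point, a few minutes per visit for staff already attending the draws, and the wording changes. The alternative costs wording only, but leaves dosing-day safety resting on the adverse-event enquiry.
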